## Non-Interventional Study (NIS) Protocol

Document Number:	c36563700-01
BI Study Number:	0135-0349
BI Investigational Product(s):	Actilyse® (Alteplase)
Title:	Effectiveness and safety of IV rt-PA treatment in Chinese AIS patients aged above 80 years: a real-world study
Brief lay title:	Alteplase treatment in elderly AIS patients
Protocol version identifier:	1.0
Date of last version of protocol:	Not applicable
PASS:	No
EU PAS register number:	EUPAS41540
Active substance:	Alteplase
Medicinal product:	Actilyse® (Alteplase)
Product reference:	Not applicable
Procedure number:	Not applicable
Marketing authorisation holder(s):	[REDACTED]
Joint PASS:	No
Research question and objectives:	
Primary objective:
 
 
• To compare the 1-year favourable neurological functional outcome (as measured by modified Rankin Scale [mRS] score , defined as mRS 0-1) of Chinese AIS patients aged > 80 years who received IV rt-PA treatment within 4.5 hours of symptom onset versus those who arrived or were admitted to the hospital within 4.5 hours of symptom onset and did not receive reperfusion therapy.
 

	
Secondary objectives:
 

• To compare in-hospital and other 1-year clinical outcomes (including any intracranial haemorrhage (ICH), all-cause mortality during hospitalisation, independence (mRS 0-2) at 1 year, distribution of mRS score at 1 year, and all-cause mortality at 1 year. Detailed description of these outcomes are provided in the section “secondary outcomes”) of elderly AIS patients who received IV rt-PA treatment within 4.5 hours of symptom onset versus those who arrived or were admitted to the hospital within 4.5 hours of symptom onset and did not receive any reperfusion therapy.

• To compare the baseline characteristics of AIS patients aged > 80 years treated with IV rt-PA within 4.5 hours of symptom onset versus AIS patients aged >80 years who arrived or were admitted to the hospital within 4.5 hours of symptom onset and did not receive reperfusion treatment in Zhejiang Stroke Quality Control Centre (ZSQCC) platform to evaluate potential channelling bias.

Country(-ies) of study:	China
Author:	
In case of PASS, add: MAH contact person:	Not applicable

**2. LIST OF ABBREVIATIONS**

AIS	Acute Ischaemic Stroke
ASD	Absolute Standardised Difference
BI	Boehringer Ingelheim
CDE	Centre for Drug Evaluation
CSCA	Chinese Stroke Centre Alliance
DMRP	Data Management and Review Plan
GPP	Good Pharmacoepidemiology Practice
ICH	Intracranial Haemorrhage
IEC	Independent Ethics Committee
IRB	Institutional Review Board
IV	Intravenous
IVT	Intravenous Thrombolysis
mRS	Modified Rankin Scale
NIHSS	National Institutes of Health Stroke Scale
NIS	Non-Interventional Study(ies)
PS	Propensity Score
PSM	Propensity Score Matching
RCT	Randomised Controlled Trials
RR	Relative Risk
rt-PA	Recombinant Tissue Plasminogen Activator
RWE	Real-World Evidence
SOP	Standard Operation Procedure
ZSQCC	Zhejiang Stroke Quality Control Centre

## 4. ABSTRACT

Name of company: Boehringer Ingelheim			
Name of finished medicinal product: Actilyse®			
Name of active ingredient: Alteplase			
Protocol date: 2 Sep 2021	Study number: 0135-0349	Version/Revision: 1.0	Version/Revision date: NA
Title of study:	Effectiveness and safety of IV rt-PA treatment in Chinese AIS patients aged above 80 years: a real-world study		
Rationale and background:	
Actilyse® was first approved for the treatment of acute ischaemic stroke (AIS) for patients aged 18-80 years. Data from recent studies have shown that patients aged > 80 years may also benefit from intravenous (IV) recombinant tissue plasminogen activator (rt-PA) when given within 4.5 hours of symptom onset.
 
All countries in the European Union including Germany, Austria and Belgium have successively approved Actilyse® to remove the age restriction of 80 years since Jun 2018. Most of the data supporting this clinical overview came from western countries. As there is limited data regarding the safety or effectiveness of IV rt-PA among Chinese AIS patients aged > 80 years, the age restriction has not been removed yet by National Medical Products Administration. However, Chinese Guidelines for Diagnosis and Treatment of AIS 2014 and 2018 removed the age restriction of 80 years in the recommendations for intravenous thrombolysis (IVT) with alteplase within 3 hours and 3 to 4.5 hours of stroke onset, respectively. In addition, Chinese AIS patients aged > 80 years have been treated with IV thrombolytic therapy in clinical practice according to local guidelines.
 
We propose to use the Zhejiang Stroke Quality Control Centre (ZSQCC) platform data to conduct a retrospective study comparing the 1-year clinical outcome of IV rt-PA treated patients versus non-reperfusion elderly (> 80 years) AIS patients.
		
Research question and objectives:	
Research question: Can Chinese AIS patients older than 80 years benefit from IV rt-PA treatment within 4.5 hours of symptom onset in a real-world clinical setting?
 
Primary objective:
 
 
• To compare the 1-year favourable neurological functional outcome (as measured by modified Rankin Scale [mRS] score, defined as mRS 0-1) of Chinese AIS patients aged > 80 years receiving IV rt-PA treatment within 4.5 hours of symptom onset versus those who
 
		

Name of company: Boehringer Ingelheim			
Name of finished medicinal product: Actilyse®			
Name of active ingredient: Alteplase			
Protocol date: 2 Sep 2021	Study number: 0135-0349	Version/Revision: 1.0	Version/Revision date: NA
		arrived or were admitted to the hospital within 4.5 hours of symptom onset and did not receive reperfusion therapy.	

Secondary objectives:
 
 
• To compare in-hospital and other 1-year clinical outcomes (including any intracranial haemorrhage (ICH), all-cause mortality during hospitalisation, independence (mRS 0-2) at 1 year, distribution of mRS score at 1 year, and all-cause mortality at 1 year. Detailed description of these outcomes are provided in the section “secondary outcomes”) of elderly AIS patients receiving IV rt-PA treatment within 4.5 hours of symptom onset versus those who arrived or were admitted to the hospital within 4.5 hours of symptom onset and did not receive any reperfusion therapy.
 
• To compare the baseline characteristics of AIS patients aged > 80 years treated with IV rt-PA within 4.5 hours of symptom onset versus AIS patients aged > 80 years who arrived or were admitted to the hospital within 4.5 hours of symptom onset and did not receive reperfusion treatment in ZSQCC platform to evaluate potential channelling.
 
 

			
Study design:	This is a NIS based on existing data from the ZSQCC platform.		
Population:	
Inclusion criteria:
 
 
• Patients registered in the ZSQCC platform from Jan 2017 to Mar 2020
 
• > 80 years of age
 
• Diagnosed with AIS at admission
 
		

# BOEHRINGER INGELHEIM Group of Companies

## NIS Protocol

### BI Study Number 0135-0349

Page 9 of 42

c36563700-01

Proprietary confidential information © 2021 Boehringer Ingelheim International GmbH or one or more of its affiliated companies

Name of company: Boehringer Ingelheim			
Name of finished medicinal product: Actilyse®			
Name of active ingredient: Alteplase			
Protocol date: 2 Sep 2021	Study number: 0135-0349	Version/Revision: 1.0	Version/Revision date: NA

 
Arrived or admitted to the hospital within 4.5 hours of symptom onset
 
If treated with IV rt-PA: received IV rt-PA within 4.5 hours of symptom onset
 
 
Exclusion criteria:
 
 
Documented IVT contraindication except age to IV rt-PA treatment according to the SmPC.
 
Missing any one of the key data (age, gender, baseline National Institutes of Health Stroke Scale [NIHSS], time of symptom onset, time of hospital arrival or admission, IVT status, time of IV rt-PA treatment)
 
Received thrombolysis agents other than rt-PA (urokinase, tenecteplase, recombinant plasminogen activator, prourokinase, streptokinase)
 
Received endovascular treatment
 
Received IV rt-PA after 4.5 hours of symptom onset
 
 
Eligible patients from the ZAQCC platform will be divided into 2 cohorts:
 
 
IV rt-PA cohort: AIS patients aged > 80 years who received IV rt-PA within 4.5 hours of symptom onset
 
Non-reperfusion cohort: AIS patients aged > 80 years who arrived or were admitted to the hospital and did not receive any reperfusion treatments
 
			
Variables:	
Primary outcome:
 
 
Favourable outcome (mRS 0-1) at 1 year
 
 
Secondary outcomes:
 
 
Any intracranial haemorrhage (ICH) during hospitalisation
 
All-cause mortality during hospitalisation
 
Independence (mRS 0-2) at 1 year
 
Distribution of mRS score at 1 year
 
All-cause mortality at 1 year
 
		

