## **9.5 STUDY SIZE**

A feasibility assessment was conducted in June 2020. The results showed that there were approximately 1561 elderly AIS patients who were treated with IV rt-PA and 1037 patients who were admitted to the hospital within 4.5 hours of symptom onset without IVT contraindication and did not receive reperfusion treatment from Jan 2017 to Mar 2020 according to the ZSQCC platform database.

A meta-analysis of RCTs showed that the 3-month favourable outcome (mRS 0-1) with IV rt-PA versus the placebo arm in patients above 80 years of age was 19.1% versus 13.1% (relative risk [RR]: 1.46). In safe implementation of thrombolysis in upper time window monitoring study, the 3-month favourable outcome for IV rt-PA treated elderly patients was 26.6%. In this study, we assume the 1-year favourable outcome for IV rt-PA treated elderly patients is 28%, with the same RR (1.46) observed in RCTs, and the 1-year favourable outcome for non-reperfusion cohort is 19.2%. With the treatment ratio 2:1 between the IV rt-PA cohort and the non-reperfusion cohort, 1106 patients in total are needed to detect the treatment difference of 8.8% with 90% power and a 2-sided alpha of 0.05. Considering a 15% rate of loss to visit, 1301 patients in total are needed. If a 2:1 match cannot reach good match in terms of the major potential confounders, we may conduct a 1:1 match instead. Considering a treatment ratio 1:1 with the same assumption described above with power of 90% at a 2-sided, 974 patients are needed to detect 8.8% treatment difference, considering 15% loss to visit, 1146 patients are needed in total.

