## **9.9 LIMITATIONS OF THE RESEARCH METHODS**

This is a NIS based on existing data. Although PSM is used, we cannot rule out the influence of unmeasured confounding factors. In this study, potential limitations of the study design can be listed as:

- Zhejiang is an economically advanced province in China. Patients in this study may not be fully representative to all AIS patients in China. We plan to compare the

baseline characteristics of patients in this study with those from CSCA to evaluate the representativeness of the population in this study.

- AIS patient data from the ZSQCC platform were reported by the stroke centre without external monitoring.
- The treatment adapted for AIS patients may be different among stroke centres.
- The completeness of the captured data and potential for misclassification of data could differ among stroke centres.
- Some important variables may not be collected in the database. For example, patients' education level was not available in the database. Another example is that patients who did not receive rt-PA treatments were not followed up at 3 months after discharge. Therefore, for outcomes at 3 months we could only describe them in the rt-PA treated cohort.

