12.1.2 Information bias?				9.9
12.1.3 Residual/unmeasured confounding? (e.g. anticipated direction and magnitude of such biases, validation sub-study, use of validation and external data, analytical methods).				NA

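### Pre-stroke disability is in no readable covariate list or the propensity model, so an imbalance left after matching can create part of the planned 8.8-point benefit on mRS 0-1

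*Protocol*

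**What the plan says.** The primary outcome is "Favourable outcome (mRS 0-1) at 1 year" (Protocol Abstract and 9.3.2.1; SAP 8.2.1). It is not set relative to the patient's function before the stroke.

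The covariates in Protocol 9.3.3 and SAP 8.3 are demographics, insurance, smoking, baseline NIHSS, onset-to-admission time, five comorbidities, three co-medication classes and hospital level. Some items apply to the rt-PA cohort only. SAP 11.1 gives a closed list for the propensity model. None of these contains pre-stroke mRS, dependency or frailty. Neither the eligibility criteria nor the key-data list (Protocol 9.2.2; SAP 7.3) mentions it. Adjustment after matching covers only baseline covariates that remain unbalanced.

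One secondary objective compares recorded baseline characteristics in the "platform to evaluate potential channelling bias". Reasons for withholding rt-PA are collected but used for description only (Protocol 9.7.1).

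Protocol 9.9 concedes: "Although PSM is used, we cannot rule out the influence of unmeasured confounding factors". Its example of an uncollected baseline variable is education level. The ENCePP checklist (Annex 2, item 12.1.3) marks as not applicable the item beginning "Residual/unmeasured confounding? (e.g. anticipated direction and magnitude of such biases". Item 10.8 answers yes on sensitivity analyses and cites Protocol 9.7.2, which is not readable in the public version. Nor is SAP 11.2.

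**The concern.** This is more specific than the usual caveat about unmeasured confounding, because the endpoint turns pre-stroke function into something close to a ceiling. A patient at mRS 2 or worse before the stroke is unlikely to be at 0-1 a year after it, whatever was given. The same characteristic may plausibly influence whether a clinician treats. Patients with a documented contraindication are excluded, so those left in the untreated cohort went untreated for other reasons.

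If untreated patients were more often disabled beforehand, the matched comparison would favour rt-PA even with every absolute standardised difference below 0.1. A larger matched sample would not help: the bias stays the same while the standard error shrinks. Protocol section 7 refers to regulatory guidance under which real-world evidence may support adding a population to a label. For that use, a significant result has to be attributable to the drug.

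**Working it through.** **Inputs from Protocol 9.5.** Rates of 28% (rt-PA) and 19.2% (non-reperfusion), a difference of 8.8 points, 90% power, two-sided 5%. Totals are 1106 at 2:1 and 974 at 1:1, or 1301 and 1146 after 15% loss. The feasibility count is 1037 eligible untreated patients.

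**Assumptions not in the documents.** d1 and d0 are the shares with pre-stroke mRS 2 or worse in the treated and untreated cohorts *after matching*. e is the chance of mRS 0-1 at 1 year in such patients, taken as 0% and 5%.

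**Step 1: the plan's own figure.** The pooled-variance two-proportion formula gives 487.2 per arm at 1:1 (974.4 in total; stated 974). At 2:1 it gives 368.2 controls (1104.7 in total, or 1107 after rounding up; stated 1106). Loss: 974/0.85 = 1145.9 and 1106/0.85 = 1301.2. The plan's sizes reproduce.

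**Step 2: false difference with no drug effect.** Let f be the chance of mRS 0-1 in patients without pre-stroke disability, set so that the untreated rate is 19.2%:

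f = (0.192 − e·d0)/(1 − d0); treated rate t = f·(1 − d1) + e·d1

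Example with d1 = 15%, d0 = 25%, e = 0: f = 0.192/0.75 = 0.256 and t = 0.256 × 0.85 = 0.2176, a false +2.6 points.

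**Step 3: how often the test rejects.** With Δ = t − 0.192, s0 the pooled standard error and s1 the unpooled one, the probability is Φ((Δ − 1.96·s0)/s1) plus a negligible opposite tail. For the example at 487 per arm: (0.0256 − 1.96 × 0.02586)/0.02585 = −0.97, which gives about 17%. The second sample size is 1037 × 0.85 = 881 per arm, the 1:1 maximum, which requires every untreated patient to be matched.

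| d1 v d0 | e | t | False difference | Rejects, 487/arm | Rejects, 881/arm |
|---|---|---|---|---|---|
| 15% v 25% | 0% | 21.8% | +2.6 | 17% | 27% |
| 15% v 25% | 5% | 21.1% | +1.9 | 11% | 17% |
| 15% v 30% | 0% | 23.3% | +4.1 | 35% | 56% |
| 15% v 30% | 5% | 22.2% | +3.0 | 22% | 35% |

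**Step 4: what would produce all 8.8 points.** Set t = 0.28, so f = (0.28 − e·d1)/(1 − d1) and d0 = (f − 0.192)/(f − e). At d1 = 15%, d0 is 41.7% (e = 0) or 47.5% (e = 5%), a gap of 26.7 to 32.5 points. For d1 between 5% and 20%, the gap runs from 25.1 points (d1 = 20%, e = 0) to 36.3 (d1 = 5%, e = 5%).

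**Step 5: tipping point if 28% v 19.2% were observed.** At 881 per arm, treating the arms as independent:

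SE(log RR) = √(0.72/(881 × 0.28) + 0.808/(881 × 0.192)) = 0.0877

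lower limit L = 1.458 × exp(−1.96 × 0.0877) = 1.228

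With e = 0 the corrected risk ratio is RR × (1 − d0)/(1 − d1), so the lower limit reaches 1 at d0 = 1 − (1 − d1)/L:

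- d1 = 5%: d0 = 22.6%, gap 17.6 points
- d1 = 15%: d0 = 30.8%, gap 15.8 points
- d1 = 30%: d0 = 43.0%, gap 13.0 points

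At 487 per arm L is 1.157, and the gap at d1 = 15% is 11.5 points. The tipping gap depends on the ratio (1 − d1)/(1 − d0), so no single gap summarises it; a curve over d1 is needed.

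**The case against.** Four points can be made for the plan.

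- *Matching on proxies.* The propensity model includes age, NIHSS, prior stroke/TIA, atrial fibrillation, other comorbidities and co-medication. These may remove part of the imbalance, and only what is left counts in the figures above. This stands. The proxies are partial, though: prior stroke/TIA does not grade disability, and SAP 10.2 counts a missing comorbidity as absent.
- *Assumed prevalences.* The documents give none, and e = 0 with 881 per arm is the extreme scenario. This stands, and is why ranges are shown.
- *Disclosure.* Protocol 9.9 already concedes unmeasured confounding and that some important variables may not be held. That is true in general terms, but it does not name this variable or give a size.
- *Unreadable sections.* Protocol 9.7.2, cited in the checklist for sensitivity analyses, and SAP 11.2 may already contain a bias analysis. This cannot be excluded.

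A reader might go further and infer three things that the documents do not support. First, that pre-stroke disability would account for the whole planned benefit: at 15% in the treated cohort that needs a gap of about 27 points or more surviving the match. Second, that the channelling objective cannot reveal this route: reasons for non-treatment are collected and may record prior dependency, although the documents do not say so. Third, that the general caveat is the plan's only response: the unreadable sections prevent that conclusion.

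**Conclusion.** The concern holds in a limited form. Pre-stroke function is missing from everything readable that could control for it, while the endpoint depends on it directly. The planned analysis can therefore favour rt-PA with all listed covariates balanced. Under the stated assumptions, a 10-point gap after matching creates roughly a fifth to 30% of the planned difference (1.9/8.8 = 22%; 2.6/8.8 = 30%). A 15-point gap creates about a third to just under a half (3.0/8.8 = 34%; 4.1/8.8 = 47%). Both raise the false-positive rate well above 5%.

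The direction, favouring rt-PA, assumes that untreated patients were the more disabled; the documents contain no data on this. They also do not say whether the platform records pre-stroke mRS. The omission is certain as far as the documents can be read; the size of the bias is not known. It should be corrected before results are seen, because a tipping-point analysis is most credible when fixed in advance.

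**What to change.** 1. If the platform holds pre-stroke mRS, add it to SAP 8.3, to the propensity model in SAP 11.1 and to the tables of standardised differences. Also tabulate how many of the recorded reasons for non-treatment refer to prior dependency.
2. Unless Protocol 9.7.2 or SAP 11.2 already does so, pre-specify in SAP 11.1 a tipping-point analysis for pre-stroke disability. For each treated-cohort prevalence d1 (for example 5%, 15% and 30%), and for a chance of mRS 0-1 in disabled patients of 0% and 5%, report the untreated-cohort prevalence d0 that brings first the lower confidence limit and then the point estimate to no effect. Present this as a curve rather than one smallest gap. Use standard errors that respect the matching, and state how the result relates to the planned conditional odds ratio, since the illustration here uses an unmatched risk ratio.
3. Report the primary conclusion together with that curve, and name pre-stroke function in Protocol 9.9.

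The cost is one SAP paragraph, one figure or table and one sentence in the protocol. Item 2 needs no new data. The small downside is that the conclusion may read less favourably.

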**BOEHRINGER INGELHEIM Group of Companies****NIS Protocol****BI Study Number 0135-0349**

Page 10 of 42

**c36563700-01**

Proprietary confidential information © 2021 Boehringer Ingelheim International GmbH or one or more of its affiliated companies

Name of company: Boehringer Ingelheim			
Name of finished medicinal product: Actilyse®			
Name of active ingredient: Alteplase			
Protocol date: 2 Sep 2021	Study number: 0135-0349	Version/Revision: 1.0	Version/Revision date: NA

Baseline characteristics (age, gender, NIHSS, etc.)

 			

Covariates:
 

Demographic and sociological characteristics

Age

Gender (male, female)

Body weight

Medical insurance status (urban employee basic medical insurance, urban resident basic medical insurance, new rural cooperative medical insurance, other insurance, no insurance)

Lifestyle related characteristics

Smoking status (current smoker, former smoker, never smoker)

Stroke severity (baseline NIHSS)

Time from symptom onset to hospital admission

For patients in the IV rt-PA cohort:

Time from symptom onset to treatment

Time from hospital admission to treatment

rt-PA dosage (dichotomised as standard dosage and low dosage)

Comorbidities at baseline

Diabetes

Coronary artery disease

Atrial fibrillation

Prior stroke/transient ischaemic attack

			

Name of company: Boehringer Ingelheim					
Name of finished medicinal product: Actilyse®					
Name of active ingredient: Alteplase					
Protocol date: 2 Sep 2021	Study number: 0135-0349	Version/Revision: 1.0	Version/Revision date: NA		
		
 
 Hypertension
 
• Co-medication at baseline (anti-platelet, oral anticoagulation, lipid lowering)
 
• Hospital level 
 
 Grade 2
 
 Grade 3
 
 
 
• Duration of hospitalization
 
• Reasons for not being treated with rt-PA for rt-PA non treatment group
 
			
Data sources:	ZSQCC platform				
Study size:	Approximately 1301 or 1146 patients, calculated by 2:1 or 1:1 treatment ratio, respectively.				
Data analysis:	
To account for potential confounding, the study cohorts (patients who received IV rt-PA and patients who did not receive reperfusion treatment) will be matched by baseline characteristics using the propensity score matching (PSM) method. The PSM aims to balance the 2 treatment cohorts on baseline covariates. The feasibility of PSM will be evaluated based on available sample size and descriptive results. If patient characteristic between the 2 cohorts are significantly different, the study design will be re-evaluated before proceeding to analysis. The Nearest Neighbour method of PSM will be used to select the matched samples. The final list of baseline characteristics in the PSM will be decided in conjunction with Boehringer Ingelheim. All the variables listed in the section covariates will be considered. Covariates including duration of hospitalization and reasons for untreated with rt-PA are only for descriptive analysis. The distribution of baseline characteristics will be presented before and after the matching process. Absolute standardized difference (ASD) between the compared groups will be calculated, in which a <math>\geq 10\%</math> ASD will be considered a meaningful difference.
 
For baseline covariates that are not sufficiently balanced after PSM, the covariates will be included in an appropriate multivariate model to adjust for those differences.
 
Main Analysis: A comparison of 1-year favourable outcome between the propensity score
				

